#### *FCT Fold Change from Baseline*

Individual FCT fold change from baseline values will be natural log transformed prior to statistical analysis. It is expected that the mean FCT log fold-change from baseline in responders is higher than that in non-responders. The difference in mean FCT log fold-change from baseline between responders and non-responders will be quantified by calculating the posterior probability that the difference exceeds zero under the Bayesian framework. The planned approach will be to assume that these participant-level FCT log fold-change from baseline values arise from normal distributions with means and variances that potentially differ for responders and non-responders. Non-informative (vague) priors will be used: e.g., a diffuse normal distribution centered at 0 with precision 1e-06 as prior for the mean, and a Gamma (1e-04, 1e-04) distribution as prior for the precision. The same priors will be used for both responders and non-responders. The second primary hypothesis

will be supported if the posterior probability that the mean FCT log fold-change from baseline of responders exceeds that of non-responders is greater than 70%. The 95% posterior credible interval will also be provided for the difference in mean FCT log fold-change from baseline between responders and non-responders.

Supportive analysis may be performed by adding to the hierarchical linear model a covariate time point to indicate whether the sample was taken before or after treatment, and an interaction term between the response and time point.

#### *ASCTFR*

Similarly, the third primary objective to compare the ASCTFR between responders and non-responders will also be addressed using a Bayesian framework to compare means between the 2 groups of participants. It is expected that on-treatment specific tumor-infiltrating cytotoxic T-lymphocytes represent a set of expanded, higher frequency clones among responders compared to non-responders. The analysis method for ASCTFR will be similar to that for the FCT fold-change from baseline: we assume that these participant-level average log frequency ratios arise from normal distributions with means and variances that potentially differ for responders and non-responders. The key quantity being estimated will be the posterior probability that the mean ASCTFR is larger in responders vs. non-responders. Non-informative (vague) priors will be used: e.g., a diffuse normal distribution centered at 0 with precision 1e-06 as prior for the mean, and a Gamma (1e-04, 1e-04) distribution as prior for the precision. The same priors will be used for both responders and non-responders. The third primary hypothesis will be supported if the posterior probability that the mean ASCTFR for responders exceeds that of non-responders is greater than 70%. The 95% posterior credible interval will also be provided for the difference in mean ASCTFR between responders and non-responders.

#### *Other Biomarker Endpoints*

Details around the analysis approach for biomarker endpoints related to the secondary and exploratory objectives are deemed out of scope for this SAP, but may be the subject of sSAPs.

### **9.6.2 Statistical Methods for Efficacy Analyses**

The chief purpose of determining efficacy for this study is to define the appropriate subsets to be compared in the evaluation of the biology of intra-tumoral changes. Participants will be separated as responder vs. non-responder, as assessed by RECIST 1.1 per investigator review.

This section describes the statistical methods that address the secondary efficacy objective (ORR, PFS and OS).

#### *Objective response rate (ORR)*

The ORR point estimate and its 95% Clopper-Pearson CI will be reported. Participants without disease assessment after the start of treatment will be considered as non-responders in ORR estimation.

*Progression-free-survival (PFS)*

The Kaplan-Meier method will be used to estimate the PFS curve. The median PFS and its associated two-sided 95% confidence interval (CI) will be estimated and reported. The Kaplan-Meier estimates of the PFS rate at 6 months and other time points of interest will also be reported. Since disease progression is assessed periodically, PD can occur any time in the time interval between the last assessment where PD was not documented and the assessment when PD is documented. For this analysis, for participants who have PD, the true date of disease progression will be approximated by the date of first assessment at which PD is objectively documented using RECIST 1.1, regardless of discontinuation of study drug. Death is always considered as a confirmed PD event. Participants without documented PD/death will be censored at the last disease assessment date. In the event that participants without documented PD/death have new anticancer treatment initiated, the participants will be considered censored at last disease assessment before new anticancer treatment.

*Overall Survival (OS)*

The Kaplan-Meier method will be used to estimate the OS curve. The median OS and its associated two-sided 95% CI will be estimated and reported. The Kaplan-Meier estimates of the OS rate at 6 months and other time points of interest will also be reported. A sensitivity analysis of OS that censors participants at the time of initiation of new anticancer treatment will also be performed. [Table 7](#) summarizes the efficacy analyses.

Table 7 Analysis Strategy for Efficacy Variables

Endpoint/ Variable (Description, Time Point)	Primary vs. Supportive Approach	Statistical Method	Analysis Populatio n	Missing Data Approach
Secondary Objective				
ORR	P	Point estimate with 95% Clopper-Pearson CI for ORR will be reported.	APaT	Participants with missing data are considered non-responders
PFS	P	Kaplan-Meier method for PFS curve estimation, and summary statistics with 95% CIs will be reported.	APaT	Censored at last assessment (before new anticancer treatment)
OS	P	Kaplan-Meier method for OS curve estimation, and summary statistics with 95% CIs will be reported.	APaT	Censored at last date
OS	S	Kaplan-Meier method for OS curve estimation, and summary statistics with 95% CIs will be reported.	APaT	Censored at last date or initiation of new anticancer treatment

Abbreviations: APaT = All Participants as Treated; ORR = objective response rate; OS = overall survival; P = Primary approach; PFS = progression-free survival; S = Supportive approach.

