#### 8.2.1.2 Tumor Imaging During the Study

The first on-study imaging assessment should be performed at 9 weeks (63 days  $\pm$  7 days) from the date of allocation. Subsequent imaging should be performed every 9 weeks (63 days  $\pm$  7 days) or more frequently if clinically indicated. After 12 months (52 weeks  $\pm$  7 days), participants who remain on treatment will have imaging performed every 12 weeks (84 days  $\pm$  7 days). Imaging timing should follow calendar days and should not be adjusted for delayed for delays in cycle starts. Imaging should continue to be performed until disease progression is identified by the Investigator (unless the Investigator elects to continue treatment and follow iRECIST), the start of new anticancer treatment, withdrawal of consent, death, or the end of the study, whichever occurs first.

Imaging should continue to be performed until disease recurrence is assessed identified by the investigator (unless the Investigator elects to continue treatment and follow iRECIST), the start of new anti-cancer treatment, withdrawal of consent, death, or the end of the study, whichever occurs first.

Objective response should be confirmed by a repeat imaging assessment. Tumor imaging to confirm PR or CR should be performed at least 4 weeks after the first indication of a response is observed. Participants will then return to regular scheduled imaging, starting with the next scheduled imaging time point. Participants who receive additional imaging for confirmation do not need to undergo the next scheduled tumor imaging if it is less than 4 weeks later; tumor imaging may resume at the subsequent scheduled imaging time point.

Per iRECIST (Section 8.2.1.5), disease progression should be confirmed by the site 4 to 8 weeks after site-assessed first radiologic evidence of PD in clinically stable participants. Participants who have unconfirmed disease progression may continue on treatment at the discretion of the Investigator until progression is confirmed by the site, provided they have met the conditions detailed in Section 8.2.1.5. Participants who receive confirmatory imaging do not need to undergo the next scheduled tumor imaging if it is less than 4 weeks later; tumor imaging may resume at the subsequent scheduled imaging time point, if clinically stable. Participants who have confirmed disease progression by iRECIST, as assessed by the site, will discontinue study treatment. Exceptions are detailed in Section 8.2.1.5.

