#### **9.4.2 Efficacy Endpoints**

##### **Secondary Efficacy Endpoints**

- 1) ORR is defined as the proportion of the participants in the analysis population who have a best response as CR or PR. Responses are based on local site review using RECIST 1.1.
- 2) PFS is defined as the time from start of treatment to the first documented PD (based on local site review using RECIST 1.1) or death due to any cause, whichever occurs first.
- 3) OS is defined as the time from start of treatment to death due to any cause. Participants without documented death at the time of the analysis will be censored at the date of last follow-up. See Section 9.6.2 for the definition of censoring.

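### The 6-month PFS rate is read early in the Week 27 scan window, so it tends to overstate freedom from true progression; a rate at 28 weeks should be added.

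*Combined protocol and SAP*

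**What the plan says.** Section 9.6.2 plans a Kaplan-Meier PFS curve, the median with its confidence interval, and landmark rates: "The Kaplan-Meier estimates of the PFS rate at 6 months and other time points of interest will also be reported". Those other time points are not specified. The same section says that progression may arise at any time between two assessments, and that "the true date of disease progression will be approximated by the date of first assessment at which PD is objectively documented using RECIST 1.1". Table 7 gives OS a supportive analysis but gives PFS none, and no interval-censored estimate is planned.

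Section 8.2.1.2 sets the scans by calendar day from allocation: "The first on-study imaging assessment should be performed at 9 weeks", then "Subsequent imaging should be performed every 9 weeks", each with a 7-day window on either side, "or more frequently if clinically indicated". Section 9.4.2 starts the PFS clock at first dose. Section 8.1.8 puts first dose no more than 3 days after allocation.

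**The concern.** Under this dating rule the PFS curve falls mainly when scans take place. A landmark just before most participants reach a scheduled scan misses the progressions that arose since the previous one. Six months sits about there relative to the third scan. A participant whose disease progresses between Week 18 and six months will usually still be counted as progression-free at six months.

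What is at stake is how one figure is read. It is the only fixed PFS time point named. In a single-arm study, a reader may take it at face value or set it against results obtained on another imaging schedule. Part of it would also depend on whether sites scan early or late within their window.

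**Working it through.** **No figure to reproduce.** The documents state no PFS median, rate or hazard shape. The calendar below comes from the documents; the sizes rest on stated assumptions.

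**Calendar**
- Third scan: 3 × 63 = day 189 from allocation, window 182 to 196.
- From first dose, 0 to 3 days later: earliest 182 − 3 = 179, latest 196 − 0 = 196.
- Six months: 365.25 / 2 = 182.6, taken as day 183.
- If scans are spread evenly over the 15 days of the window, the share after day 183 is 13/15, 12/15, 11/15 and 10/15 for lags of 0, 1, 2 and 3 days. That is 87% down to 67%, averaging 46/60 = 76.7%.

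**Size with scheduled scans only.** Assume exponential PFS, S(d) = exp(−ln 2 × d / median), with one month = 30.44 days. The mean lag is 1.5 days, so the second scan is on average at day 126 − 1.5 = 124.5 from first dose and the third at 189 − 1.5 = 187.5.

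- Excess at day 183 ≈ 0.767 × [S(124.5) − S(183)]
- Excess at day 196 ≈ S(187.5) − S(196)

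| Assumed median (months) | S(124.5) % | True S(183) % | Excess at day 183, formula | Reported 6-month rate, simulated % | Excess at day 196, formula |
|---|---|---|---|---|---|
| 3 | 38.9 | 24.9 | 10.7 | 35.7 | 1.5 |
| 4 | 49.2 | 35.3 | 10.7 | 46.1 | 1.6 |
| 5.5 | 59.7 | 46.9 | 9.8 | 56.8 | 1.6 |
| 8 | 70.2 | 59.4 | 8.3 | 67.7 | 1.4 |
| 12 | 79.0 | 70.7 | 6.4 | 77.2 | 1.1 |

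The simulation used 400,000 participants per median, even scan windows and a 0 to 3 day lag. Its excess is the simulated rate minus the true rate, for example 56.8 − 46.9 = 9.9 points at a 5.5-month median. Formula and simulation agree to about 0.1 point.

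**Size when some events do not wait for a scheduled scan**
- 15% of events are exactly dated deaths: about 5.5 to 9 points.
- The same, and 20% to 35% of events are found off-schedule within 14 days of onset: 3.4 to 7.2 points.
- The same again with a falling hazard (Weibull shape 0.6): 2.6 to 4.4 points.

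**Sensitivity to convention.** With scheduled scans only, reading six months as day 182.6 instead of 183 raises the excess slightly: 11.7, 10.9, 9.1 and 7.0 points at medians of 3, 5.5, 8 and 12 months.

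**Scale.** With 60 participants, the 95% half-width for a rate of 50% is 1.96 × √(0.5 × 0.5 / 60) = 12.7 points.

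**Later landmarks.** Twelve months is day 365. The last scheduled scan before it is Week 45 (day 315). Even on a 9-week interval the next window opens no earlier than 378 − 7 − 3 = day 368 from first dose. A 12-month rate would have the same problem.

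**The case against.** **The estimate is not biased for the endpoint as defined.** A reader might infer that the Kaplan-Meier rate is wrong for the SAP's own PFS. It is not. Section 9.4.2 reads "PFS is defined as the time from start of treatment to the first documented PD (based on local site review using RECIST 1.1"), and scan timing does not bias the estimate of time to documented progression. The excess is against latent progression time, and Section 9.6.2 says openly that the scan date only approximates it. This stands, and it limits the point to where the curve is read.

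**The size is not a fact of the plan.** A reader might quote a fixed number of points. The documents supply no PFS assumption, and several routes register events between scheduled scans: deaths, clinically indicated scans, discontinuation scans (Section 8.2.1.3), response-confirmation scans, and palliative radiation, which Section 6.5.2 counts as progression for PFS. These reduce the excess. It stayed upward in every scenario run.

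**Six months is not the worst place.** A reader might infer that it is. Day 183 is inside the window, and 13% to 33% of third scans have already taken place. In the scheduled-scan simulation with a 3-month median, the excess is 13.0 points at day 178 against 10.7 at day 183. For the same reason the 6-month rate is not simply the 18-week rate.

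**Little depends on it.** No test, threshold or decision uses the rate. Section 9.8 calls all analyses exploratory, and Section 9.6.2 says that efficacy mainly serves to define the responder groups. The median and full curve are reported too, and no cross-trial comparison is planned. This stands and sets the severity.

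**Six months is conventional and matches the OS landmark.** This is a fair reason to keep the rate, but not to report it alone.

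**Conclusion.** The point holds as a low-severity improvement. The one named PFS landmark falls early in the third-scan window, so for most participants the reported rate rests on scheduled scans through Week 18 and leans upward against true progression.

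Under assumed medians of 3 to 12 months, the excess is about 6 to 11 points with exponential PFS and scheduled scans only. It is about 3 to 7 points when some events are exactly dated deaths or are found off-schedule, and a steeply falling hazard takes it slightly lower. At day 196 it is at most about 1.6 points. The direction and the calendar follow from the documents; the sizes rest on the assumed medians, hazard shape, evenly spread scan days and share of off-schedule events.

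The documents do not support calling the analysis invalid, attaching one definite bias figure to it, or requiring that the 6-month rate be dropped.

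**What to change.** In Section 9.6.2, add the Kaplan-Meier PFS rate at 28 weeks (day 196, the end of the Week 27 imaging window) as the landmark to interpret. Set any later PFS landmark at the end of a scan window in the same way. If the 6-month PFS rate is kept for convention, report it beside the 28-week rate with a note that it mainly reflects scans through Week 18. Leave the 6-month OS rate unchanged, because deaths are dated exactly.

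The cost is a line or two of SAP text and one extra reported figure, with no new data and no change to the imaging schedule. The 28-week rate will be less favourable than the 6-month rate, because it counts the progressions found at the third scan. With scheduled scans only and a 5.5-month median, the simulated 6-month rate is 56.8%, against about S(187.5) = 46.0% at 28 weeks.

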### 9.6.3 Statistical Methods for Safety Analyses

Safety and tolerability will be assessed by clinical review of all relevant parameters including AEs, laboratory tests, and vital signs.

Descriptive summary statistics will be provided for safety endpoints. See [Table 8](#) for the list of safety endpoints to be summarized. For continuous measures such as changes from baseline in laboratory tests and vital signs, summary statistics for baseline, on-treatment, and change from baseline values will be provided in table format. Additional safety endpoints may also be summarized, as deemed clinically appropriate.

Table 8 Analysis Strategy for Safety Parameters

Safety Endpoint †	Descriptive Statistics
Any AE	X
Any Grade 3-5 AE	X
Any Serious AE	X
Onset and Duration of First Grade 3-5 AE	X
Any Drug-Related AE	X
Any Serious and Drug-Related AE	X
Any Grade 3-5 and Drug-Related AE	X
Discontinuation due to AE	X
Death	X
Specific AEs, SOCs	X
Change from Baseline Results (Labs, Vital Signs)	X

Abbreviations: AE = adverse event; SOC = system organ class

†Adverse events refer to both Clinical and Laboratory AEs.

Note: X = results will be provided.

### 9.6.4 Summaries of Baseline Characteristics, Demographics, and Other Analyses

The number and percentage of participants screened, allocated, the primary reasons for screen failure, and the primary reasons for discontinuation will be displayed. Demographic variables (such as age), baseline characteristics, and prior and concomitant therapies will be summarized either by descriptive statistics or categorical tables.

### 9.7 Interim Analyses

During the course of the study, preliminary analyses of biomarker, efficacy and safety endpoints may be performed as data become available. The primary purpose of these analyses is to provide an early assessment of the study objectives. There is no intention to change the conduct of the current study based on the results of these analyses.

The final analyses will be carried out after all participants have had a 90-day follow-up after the end of treatment (unless lost to follow-up). If, by that time, the death rate is <70%, for OS and OS-related analyses, the final analyses will occur after death has occurred in

approximately 70% of the participants (~42 deaths). If the estimated interval between the 2 analyses is less than 3 months, then the first analysis may be delayed and both analyses will be conducted at the later of the two.

## 9.8 Multiplicity

As all analyses are exploratory in nature, no multiplicity adjustments will be applied.

## 9.9 Sample Size and Power Calculations

### 9.9.1 Sample Size and Power for Biomarker Analyses

This study will enroll approximately 60 participants. Based on response rates observed previously for melanoma patients, it is assumed that the response rate is ~30%.

For the endpoints of the primary objectives, there is no pre-specified difference in the means of prior interest. Hence, the principal summary of results around the study objectives will be via the posterior probability that the mean difference exceeds 0 in the direction of responders showing the higher mean. For the primary objectives, the posterior probability threshold to claim statistical significance is set as 70% (or a ~2-to-1 odds), which is a reasonable level of certainty addressing these objectives.

**Table 9** shows the power to detect a difference in mean baseline FCT between responders and non-responders, assuming a few different sample sizes and true differences. It is assumed that baseline FCT in non-responders follows a Beta distribution with alpha and beta parameters equal to 0.022 and 1, respectively, which puts ~95% of baseline FCT values below 0.10. True mean differences shown were obtained by selecting higher values of the alpha parameter in the responders' distribution, relative to non-responders, while keeping the beta parameter fixed at 1. Bayesian models were fit allowing for different parameter values of responders and non-responders. The results suggest that for a true mean difference at or above 0.10 and at least 10 responders, we expect to observe  $\geq 90\%$  power (with the assumed Beta distributions).

Table 9 Power for Baseline FCT

N Responder	N Non-Responder	True Mean Difference: $\delta^a$	% Power b
10	50	0.05	68
		0.10	90
15	45	0.05	80
		0.10	96
20	40	0.05	83
		0.10	98

a. Assuming that baseline FCT in non-responders follows a Beta distribution with alpha and beta parameters equal to 0.022 and 1, respectively, which puts 95% of baseline FCT values below 0.10. Mean differences shown were obtained by selecting higher values of the alpha parameter in the responders' distribution, relative to non-responders, while keeping the beta parameter fixed at 1.

b. Power is defined as  $\text{Prob}(\text{PP}_{(\delta>0)} > 70\%)$ ; computed over 500 trial simulations.

**Table 10** below provides the power for detecting a difference in mean FCT log fold-change from baseline and ASCTFR between responders and non-responders. A common standard deviation for the responders and non-responder was assumed for simplicity, although the Bayesian models were fit allowing for unique standard deviations. It is shown that with at least 10 responders, for effect sizes at or above 0.50, we expect to observe  $\geq 80\%$  power.

Table 10 Power for FCT Log Fold-Change From Baseline and ASCTFR

N Responder	N Non-Responder	True Mean Difference: $\delta^a$	% Power b
10	50	0.25	55
		0.50	81
15	45	0.25	61
		0.50	88
20	40	0.25	64
		0.50	90

a. Assuming standard deviation of 1 for each of the responder and non-responder groups, as would result if first dividing each of the non-responder and responder groups by their respective true (albeit unknown) standard deviations, and so this  $\delta$  is essentially the effect size for this exercise.  
 b. Power is defined as  $\text{Prob}(\text{PP}_{(\delta>0)} > 70\%)$ ; computed over 500 trial simulations.

As an illustration of precision associated with secondary and exploratory biomarker related objectives that may involve a large set of features being compared between responders and non-responders, **Table 11** presents the power for comparing features between these 2 groups testing for significance at a false discovery rate (FDR) of 0.20.

Table 11 Power for Other Biomarker Endpoints

N Responder	N Non-Responder	Effect Size a	% Power b
10	50	0.50	12.3
		0.75	30.7
		1.00	59.0
		1.50	95.4
15	45	0.50	16.7
		0.75	44.3
		1.00	75.4
		1.50	98.7
20	40	0.50	20.9
		0.75	54.7
		1.00	82.7
		1.50	99.7

a. Standardized difference in the biomarker means between responders and non-responders.  
 b. Testing for significance at an FDR of 0.20 and assuming 90% of hypotheses are null and 10% have the given effect size.

